6.6 Potential Risks and Benefits

Based on early studies of FT218, it is possible to predict some of the discomforts and risks. The data suggest that the potential risks of FT218 are likely to be manageable and will be monitored like Xyrem. Clinical studies with Xyrem have yielded detailed information of its safety profile. Xyrem is approved by the FDA in the US and EMA for the treatment of subjects with narcolepsy. The potential risks of FT218 from PK studies in humans have been discussed in the

summary from the Phase 1 safety study (discussed in [Section 6.3](#)) and to date are consistent with and similar to what has been previously reported with sodium oxybate.

Clinical safety of Xyrem has been established and forms the basis for the FT218 safety plan. All causality and treatment-related events for Xyrem include: abdominal pain, diarrhoea, nausea, vomiting, fatigue, peripheral oedema, anorexia, dizziness, headache, abnormal dreams, confused state, nightmare, sleep walking and enuresis. The most commonly identified AEs for sodium oxybate are nausea, dizziness and headache. In terms of AEs where there was a dose response relationship, these AEs included nausea, vomiting, paraesthesia, disorientation, irritability, disturbance in attention, feeling drunk, sleepwalking and enuresis. These events are most pronounced at the higher, 9.0 g dose, and in some cases related to the 7.5 g dose. The up-titration methods, as used with Xyrem, to maximum dose, are thus appropriate to establish safety and tolerability in study subjects who will participate in this clinical study.

The safety profile of Xyrem is thus well characterized. The safety profile, as described in the Xyrem approved labelling supports the safety of the FT218 study formulation. In addition, all necessary precautions and warnings related to subject self-care and self-monitoring for any signs and symptoms of respiratory or CNS depression, alcohol consumption, contraindicated medications, driving and use of heavy machinery apply to FT218. The proprietary extended-release oral suspension technology used for FT218 is well established. The technology is the same as that used for the marketed product Coreg CR (carvedilol, NDA 022012) for the treatment of hypertension, left ventricular dysfunction and mild to severe heart failure. This has been marketed in the US since 2007.

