10.1.2 Safety Assessments

10.1.2.1 Adverse Events

Adverse Event Definition

An AE is defined as any untoward medical occurrence in a clinical study subject administered a medicinal product which does not necessarily have a causal relationship with this treatment. Adverse events may include, but are not limited to the following: abnormal test findings, clinically significant signs and symptoms, hypersensitivity, any signs and/or symptoms from: drug overdose, drug administration/reconstitution error, any drug misuse, accidental exposure withdrawal, and or interactions, and exposure in utero.

Symptoms and signs of clinical and functional deterioration as defined in study efficacy assessment criteria for subjects with NT1 and NT2 will be not be captured as AEs. These signs and symptoms will be captured in the context of efficacy assessments via the ePRO enabled Sleep and Symptom Daily Diary, CGI rating of sleepiness, and on overnight PSG and next-day 5 hour nap MWT and will be reported as part of the efficacy analysis.

They include:

- Excessive daytime sleepiness
- Number of cataplexy attacks
- Disturbed nocturnal sleep
- Nightly arousals
- Sleep quality
- Refreshing nature of sleep
- Sleep paralysis

All other signs and symptoms of clinical and functional deterioration as they relate to the underlying diagnosis of narcolepsy (NT1 and NT2), study drug, and concomitant medications, or other will be recorded as AEs.

It is the responsibility of the investigator to document all AEs that occur during the study. AEs should be reported on the appropriate page of the eCRF.

Assessment of Severity

Each AE will be assigned a category by the investigator as follows:

- Mild:** An AE that is easily tolerated by the subject, causes minimal discomfort, and does not interfere with everyday activities
- Moderate:** An AE that is sufficiently discomforting to interfere with normal everyday activities; intervention may be needed
- Severe:** An AE that prevents normal everyday activities; treatment or other intervention usually needed

If there is a change in severity of an AE, it must be recorded as a separate event.

Assessment of Causality

For each recorded AE or SAE, the investigator or designee must make an assessment of causality based on the following criteria to determine the relationship between the AE and study drug:

Classification	Investigator's Judgement	Definition

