1.1 STUDY RATIONALE

This study was designed as a pivotal efficacy study. The background data used to design the trial was obtained from a Phase I (PKFT218-1301) pharmacokinetic study in healthy volunteers. In that study the 4.5 g FT218 formulation was associated with a safety profile and total exposure similar to the reference marketed drug product, Xyrem®. Also, no safety concerns emerged with the FT218 formulation at 6 g and 7.5 g. The study confirmed the expected PK properties of the FT218 formulation, i.e. a drug release over 6 hours, a lower C_{max} and a residual plasma level at 8 hours after intake that was not significantly different from Xyrem®. These results indicate that the FT218 formulation should be as safe as Xyrem®. Overall, the PK profile of FT218 at 4.5 g, 6 g, and at 7.5 g supports the hypothesis that the IMP is as safe as the reference, Xyrem®.

The forced up-titration design is intended to inform an appraisal of the benefits and risks of increasing doses. Three target therapeutic dose levels will be tested since a concentration/response relationship has not been established. The 6 g, 7.5 g and 9 g doses were selected for their safety and efficacy profile in treating patients with EDS and cataplexy; the study formulation has been found to be safe at 4.5 g, 6 g and 7.5 g in healthy volunteers. The up-titration schedule from 4.5 g/night to 6 g/night is based on the dosage schedule recognized as safe with the reference product. Further 1.5 g increments commence after a period sufficiently long to permit evaluation of efficacy. Subjects remain on the 6 g dose for two weeks, on the 7.5 g dose for five weeks and on the 9 g dose for five weeks.

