2.1.3 SAFETY OBJECTIVE

To evaluate the relative safety of the 6 g, 7.5g and 9 g doses of FT218 compared to placebo.

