4.7 SAFETY ANALYSES

Safety evaluations will be performed on the safety population using the actual treatment administered.

Adverse events will be identified as treatment-emergent (TEAE) if the event occurs or increases in severity after the first dose of study medication is taken. Adverse events will be identified as mild, moderate or severe and related to the treatment as reported on the CRF. The adverse events will be assigned a preferred term (PT) and a system organ class (SOC) according to the Medical Dictionary for Regulatory Activities (MedDRA), latest version. In counting the number of events reported, a continuous event, i.e., an event reported more than once and which did not cease, will be counted only once with the worst recorded severity. Non-continuous AEs reported multiple times by the same subject will be counted as multiple events. AEs will be assigned to the period of the study corresponding to the time of onset. Events presenting immediately prior to the first dose of study medication that do not worsen in severity, will not be included. In deriving the tabulation relating to preferred term reporting, the severity of a recurrent AE will be taken to be the most severe and the relationship to study medication as the most probable within the relevant period of the study. Total exposure to FT218 will be determined in terms of number of days and dose.

Laboratory data will be summarized in terms of the proportions of patients with clinically notable abnormalities using normal ranges. Shift tables will tabulate baseline to most extreme post baseline values. Summary statistics of raw data and change from baseline values will be obtained including means, medians, standard deviations and ranges will be produced.

The summaries will include subjects in the safety population who have had at least one laboratory test performed after the first study drug administration with an available baseline laboratory value. Baseline values will be measured as the last available measure before taking study drug.

[REDACTED]

[REDACTED]

[REDACTED]

[REDACTED]

[REDACTED]

[REDACTED]

[REDACTED]

[REDACTED]

[REDACTED]

[REDACTED]

[REDACTED]

[REDACTED]

[REDACTED]

[REDACTED]

[REDACTED]

[REDACTED]

[REDACTED]

[REDACTED]

[REDACTED]

[REDACTED]

[REDACTED]

[REDACTED]	[REDACTED]	[REDACTED]
[REDACTED]	[REDACTED]	[REDACTED]
[REDACTED]	[REDACTED]	[REDACTED]
[REDACTED]	[REDACTED]	[REDACTED]
[REDACTED]	[REDACTED]	[REDACTED]
[REDACTED]	[REDACTED]	[REDACTED]

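### SAP 4.7 places an AE that worsens after up-titration, at its worst severity, under the lower dose at which it began

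*SAP*

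**What the plan says.** SAP 4.7 has three rules that bear on this.

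- Counting: a continuing event that is reported repeatedly and "which did not cease, will be counted only once with the worst recorded severity".
- Period: "AEs will be assigned to the period of the study corresponding to the time of onset".
- Recurrent AEs in the preferred-term tabulation: "the severity of a recurrent AE will be taken to be the most severe and the relationship to study medication as the most probable". The limit to a period stands at the end of this rule ("as the most probable within the relevant period of the study") and in neither of the other two.

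Protocol 10.1.2.1, on severity, says: "If there is a change in severity of an AE, it must be recorded as a separate event".

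The SAP's safety objective (2.1.3) is set by dose: "To evaluate the relative safety of the 6 g, 7.5g and 9 g doses of FT218 compared to placebo". SAP 4.1 calls for descriptive statistics by dose group, and SAP 4.1.5 sets out display groups for 9 g, 7.5 g and 6 g, each with its matching placebo period.

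On Week 1 (4.5 g), SAP 2.3 with its Table 1, protocol 9.2.1 and protocol Appendix 17.2 all place it in Period 3a. SAP 4.1.5 labels the 6 g group as Period 3a but gives it weeks 2-3 only, and SAP 4.1.3 also uses weeks 2 and 3 for 6 g.

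**The concern.** Each SAP 4.7 rule is ordinary by itself. In a forced-titration trial the combination is a problem, because the dose changes while an AE is still running. The counting rule carries forward the worst severity, and the period rule fixes the AE to the dose at which it began. Severity that was reached at a higher dose is then reported under a lower one.

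This matters because of what the trial sets out to learn. SAP 1.1 says: "The forced up-titration design is intended to inform an appraisal of the benefits and risks of increasing doses". Protocol 6.6, on the AEs of sodium oxybate that show a dose response, says: "These events are most pronounced at the higher, 9.0 g dose, and in some cases related to the 7.5 g dose". A rule that can move severity out of the 9 g column weakens the table meant to show that pattern. It also removes the distinction that the protocol's separate-record requirement preserves in the database.

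**Working it through.** **Inputs.** Dosing schedule: 4.5 g for 1 week, 6 g for 2, 7.5 g for 5, 9 g for 5 (SAP 2.2). Display groups: weeks 2-3, 4-8 and 9-13 (SAP 4.1.5). Rules: SAP 4.7 and protocol 10.1.2.1.

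**1. The plan's own figures.** 1 + 2 + 5 + 5 = 13 weeks on drug, or 13 × 7 = 91 nights. The display groups cover 2 + 5 + 5 = 12 weeks. Both agree with protocol 6.5 (12 weeks of evaluation, 13 on drug). The one treatment week outside the display groups is Week 1.

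**2. One AE under each rule.** Suppose an AE starts mild in Week 5 (7.5 g), does not stop, and becomes severe in Week 9 (9 g).

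| Rule | 7.5 g column | 9 g column |
|---|---|---|
| SAP 4.7, counting and period rules together | 1 severe | none |
| Separate record (protocol 10.1.2.1), each with its own start date | 1 mild | 1 severe |

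The period limit does not rescue the first row, because it is written for recurrent AEs and this one never stopped. Nor does the treatment-emergent definition in SAP 4.7, which measures worsening against the first dose and not against each dose step.

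**3. How many paths are affected.** With four dose levels taken in rising order, the possible pairs of onset dose and dose at worst severity number 4 + 3 + 2 + 1 = 10. Worst severity comes at a higher dose than onset in 3 + 2 + 1 = 6 of them. One of the six (4.5 g to 6 g) lies inside Period 3a, where assignment by period cannot separate the doses at all. In the other 6 − 1 = 5, severity is shown under an earlier dose period; in three of these it was reached at 9 g. No path moves severity to a higher dose, because the scheduled dose never falls. These are counts of paths, not of AEs.

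**4. Window of exposure to the rule.** Nights before the step to 9 g: (1 + 2 + 5) × 7 = 56, and 56/91 = 61.5%. An AE that starts on any of these nights and continues could carry severity reached at 9 g back to a lower dose. This bounds when such an AE can begin; it does not measure bias.

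**5. Week 1.** If AEs are assigned by period and Period 3a is weeks 1-3, the 6 g column holds 7 nights at 4.5 g and 14 at 6 g: 7/21 = 33.3%. The matching placebo column also takes in Week 1. If AEs are assigned by weeks 2-3 instead, Week 1 (7/91 = 7.7% of nights) has no dose column.

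**The case against.** The strongest reply is that no harmed table is visible. The counting rule opens by limiting itself to the number of events reported, no severity-by-dose table is specified in the readable text, and redacted blocks follow SAP 4.7. Protocol 7.3 states the safety objective by arm, and protocol 11.4.1 describes summaries by arm. If the worsening record keeps its own start date, the SAP's period rule already puts it under the higher dose. SAP 4.7 does not define recurrent, so the period limit might be meant more widely.

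Much of this stands, and it limits the point to by-dose event and severity summaries. It does not remove it. SAP 4.1 and 4.1.5 direct summaries by dose, and SAP 2.1.3 sets the objective by dose. The period rule carries no limiting clause. A worsening record for an AE that never stopped is just what the counting rule merges into a single event, and nothing says that the later start date survives the merger.

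On Week 1, SAP 4.1.3 points to weeks 2 and 3, and the SAP 4.1.5 label can be read as the weeks 2-3 part of Period 3a. That makes the inconsistency small. It remains because SAP 4.7 assigns AEs by period.

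A reader might go further in three ways that the documents do not support:

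- That the SAP has no rule for placing AEs. It has one, by onset; the fault is what that rule does to an AE that worsens.
- That AEs are lost, Week 1 AEs in particular. SAP 2.6.3 tabulates all AEs, and the listings in SAP 4.1.5 show all eCRF data.
- That the distortion of the dose-placebo comparison can be put in figures. The documents give no AE counts by severity, and the same rule applies to placebo in the matching periods, so any net effect depends on how much more often AEs worsen on drug.

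**Conclusion.** The point holds in limited form. SAP 4.7, read as written, shows an AE that worsens after up-titration at its worst severity under the dose of onset. This conflicts with the separate-event record in protocol 10.1.2.1 and can understate dose-related severity at 9 g. The direction follows from the rising schedule. The size is unknown, since the documents do not say how many AEs continue and worsen across a dose step.

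The conclusion assumes that by-dose AE summaries will be produced, as SAP 4.1 and 4.1.5 indicate, and that no redacted table shell already settles the matter. Arm-level totals, AEs that start at 9 g, listings and all efficacy inference are unaffected. Week 1 is a secondary inconsistency. Overall severity: minor to moderate.

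**What to change.** In SAP 4.7, keep the overall event count as written and add for by-dose summaries: *Each new AE and each recorded worsening is tabulated under the dose period in which it began, using the worsening record's own start date; severity is the worst within that dose period.* Footnote the tables to say that dose columns need not sum to the overall count.

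In SAP 4.1.5, for safety tables only, assign AEs by week and show Week 1 (4.5 g and placebo) separately, so that the 6 g and matching placebo columns hold weeks 2-3 only.

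The cost is wording and table shells. No new data are needed, because the protocol already requires the separate record. The drawback is that one AE can appear under more than one dose. Dose remains confounded with time on drug under any rule, so the by-dose tables stay descriptive. The change should be made before unblinding, so that the placement of worsened AEs is not chosen with the results in view.
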